PROTOCOL TITLE: Randomized Placebo Controlled Trial of Intravenous N-Acetylcysteine for the Treatment of Acute Ischemic Stroke

PROTOCOL TITLE:

Randomized Placebo Controlled Trial of Intravenous N-Acetylcysteine for the Treatment of Acute Ischemic Stroke

PRINCIPAL INVESTIGATOR:

Name: [name]

Department: Emergency Medicine

[contact]

Email Address: [contact]

FDA IND:

#145,538

VERSION NUMBER:

1.6

DATE:

10/24/2023

Table of Contents

1) Protocol Title	3
2) HSC Review History	3
3) Investigator	3
4) Objectives	3
5) Lay Summary	3
6) Background.....	4
7) Setting of the Human Research	5
8) Resources Available to Conduct the Human Research	5
9) Prior Approvals	6
10) Study Design	6
a) Inclusion and Exclusion Criteria	9
b) Local Number of Subjects	9
c) Study-Wide Number of Subjects	10
d) Study Timelines.....	10
e) Study Endpoints.....	10
f) Procedures Involved in the Human Research	10
g) Data and Specimen Banking	12
h) Data Management.....	12
i) Confidentiality.....	12
j) Provisions to Monitor the Data to Ensure the Safety of subjects	12
k) Withdrawal of Subjects	15
11) Risks to Subjects	15
12) Potential Benefits to Subjects.....	15
13) Provisions to Protect the Privacy Interests of Subjects	15
14) Compensation for Research-Related Injury	16
15) Economic Burden to Subjects	16
16) Consent Process.....	16
17) Process to Document Consent in Writing	17
18) Drugs or Devices	17
19) Multi-Site Human Research	18
20) Community-Based Participatory Research.....	18
21) Sharing of Results with Subjects.....	18
22) Bibliography	18

1) Protocol Title

Randomized Placebo Controlled Trial of Intravenous N-Acetylcysteine for the Treatment of Acute Ischemic Stroke

2) HSC Review History

Version 1.5 dated 6/16/2021: NAC dosing regimen changed to complete the 2-bag regimen in 20 hours. Modified regimen will infuse a total 50 mg/kg/hr N-AC over 4 hours for a total of 200 mg/kg following by 100 mg/kg over 16 hours.

Version 1.6 dated 10/24/2023: Inclusion criteria changed to allow screening and enrollment of subjects with at least an NIH Stroke Scale (NIHSS) of 5. Use predetermined enrollment caps of 39 subjects 0in each group: moderate (NIHSS = 5-15), moderate to severe (NIHSS = 16-20) and severe stroke (NIHSS = 21-42).Population target revised to 117.

3) Investigator

[name]

4) Objectives

To determine the efficacy of a 20-hour intravenous N-Acetylcysteine regimen in patients suffering from acute ischemic stroke.

5) Lay Summary

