The FDA has reviewed the study and gave an FDA IND (#145,538). Approved was also given by the research divisions of Cumberland Pharmaceuticals (Cumberland Pharmaceuticals have agreed to donate N-acetylcysteine for the study).

10) Study Design

1) The treating ED physicians (other than the investigator or coinvestigators) will identify potential subjects in the Emergency Department at Harbor UCLA via initial evaluation (standard of care) including blood draw for a standard CVA panel (CBC, Chemistries, PT, PTT, neuronal specific enolase, s100b) and brain imaging. Subjects who present with neurological deficits consistent with stroke without hemorrhage less than 24 hours since symptom onset will be asked to whether they would be interested in participation in a research in our study and if so, the treating ED physician will contact investigators or study team member. Investigators or study team member may access medical record to confirm eligibility before approach subject.

If treating physician is member a co-investigator/ study team member, s/he will approach subject about participation once deemed to meet eligibility criteria. (See inclusion and exclusion criteria below). Informed consent will be obtained for all subjects either from the subjects themselves or if they do not have capacity, from their legally authorized representative (See Section 16 below).

2) Each subject will undergo, as part of standard of care, evaluation and assessment using the National Institutes of Health Stroke Scale (NIHSS) and the Modified Rankin Scale (MRS) which have been similarly used in the European Cooperative Acute Stroke Study III, ECASS III (3). The NIHSS is a 15-item scale that measures the level of neurologic impairment. The MRS is a measure of disability with scores ranging from 0 (no symptoms at all) to 6 (death). Individuals must have an NIHSS of at least 5 to be eligible for this study. This data will be recorded for study purposes using a standard data collection sheet.

3) Subjects will receive standard of care with the study intervention being considered an “add-on” therapy. Thirty minutes after enrollment, eligible subjects will be randomized into one of two arms: placebo or NAC.

PROTOCOL TITLE: Randomized Placebo Controlled Trial of Intravenous N-Acetylcysteine for the Treatment of Acute Ischemic Stroke

Any patient receiving t-PA who enrolls in the study will have their study drug infusion delayed by 24 hours after the completion of the t-PA infusion.

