Our patients tend to be economically disadvantaged but since there are no financial incentives either for the patient or for the investigators, this bias has been minimized. Patients will receive the same care whether they participate in the study or decline.

Exclusion Criteria:

- Evidence of hemorrhagic stroke on initial CT scan
- Need for thrombectomy as determined by the treating neurologist
- Known allergy to NAC
- Protected populations, including age < 18, known pregnancy, and prisoners
- Patients who are DNR/DNI at the time of presentation with a short life expectancy

b) Local Number of Subjects

The total number of local subjects will be 117 (39 subjects with moderate stroke = NIHSS 5-15; 39 subjects with moderate to severe stroke = NIHSS 16-20; 39 subjects with severe stroke = NIHSS = 21-42)

This number was derived using a group size analysis based on previous work on oral NAC for ischemic stroke (37) and a hypothesis of finding no

difference (defined as a change in NIHSS < 4) between NIHSS scores at 90 days. With a power of 0.80 and an alpha 0.05 we would need 47 subjects in each group. Assuming a dropout rate of 25% or lost to follow-up, we would enroll 59 in each group for a total of 117.

(Group sample sizes of 47 and 47 achieve 81% power to detect a difference of 4.0 using a one-sided Mann-Whitney U or Wilcoxon Rank-Sum test assuming that the actual data distribution is normal when the significance level (alpha) of the test is 0.05 and the standard deviation is 7.4 in both groups.)

c) Study-Wide Number of Subjects

This is a single center study at the Harbor-UCLA Medical Center.

d) Study Timelines

Estimated time to complete enrollment is December 2025. Review of the neurology services revealed that Harbor-UCLA typically sees 20 patients per month that would be eligible for the study.

e) Study Endpoints

The primary study endpoint will be comparison between groups (NAC treated group versus treatment) of the NIHSS at 90 days.

Secondary endpoints include changes in the MRS, GOS, BI, and blood tests at 30 days and 90 days, as well as MRI data including changes in brain volume and gliosis at 90 days.

f) Procedures Involved in the Human Research

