If subject is deemed incapable of decision-making or unable to physically sign a consent document, consent will be sought from the subject’s the Legally Authorized Representative (as per HRP-013 SOP LARs, Children, Guardians). This individual will complete the Self-Certification of Surrogate Decision Makers form (Appendix 3) for documentation.

Study participation will be discussed with both the patient and the physician of record/primary medical providers. Patient capacity to make decisions will be determined by the primary medical providers per routine. The study team will also determine each patient’s (potential subject’s) decision making capacity for participation in the study. Patients without capacity to make decisions and who lack a surrogate decision maker will be excluded from the study. Surrogate decision makers will be informed about the study in the same way as described above and offered to provide consent for the patient to enroll in the study.

If and when a subject regains their capacity for decision-making, consent for continued participation in the study will be sought. The standard operating procedure for informed consent will be followed (SOP: Informed Consent Process for Research, HRP-090).

17) Process to Document Consent in Writing

We are following “SOP: Written Documentation of Consent (HRP-091).”

Individuals who are not yet adults, pregnant women, and prisoners will be excluded in this study. Other vulnerable subjects, such as students, subjects with limited or no treatment options, and socially and economically disadvantaged, may be included in this study. This study does not involve more than minimal risk to the subject.

18) Drugs or Devices

N-Acetylcysteine and placebo. Study drugs will be stored, handled and dispensed by an ED pharmacist who is working at the time of study enrollment.

[name]., the ED Pharmacist will maintain drug accountability logs in compliance with FDA regulations. She will instruct other ED pharmacists about the study and the randomization log which will

be kept in the pharmacy room in the ED. She will also create study drug labels to keep the nurses, physicians and patients blinded to the study medication.

19) Multi-Site Human Research

N/A

20) Community-Based Participatory Research

This is not a community-based participatory research project.

21) Sharing of Results with Subjects

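### The primary comparison of day-90 NIHSS does not use enrolment NIHSS, although it is recorded for every subject; pre-specifying a baseline-adjusted test would gain power at almost no cost

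*Combined protocol and SAP*

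**What the plan says.** Section 10(e) defines the primary endpoint: "The primary study endpoint will be comparison between groups (NAC treated group versus treatment) of the NIHSS at 90 days". No covariate, stratum or model is attached to it.

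A test is named only in the parenthetical sample-size note in section 10(b), which computes power "using a one-sided Mann-Whitney U or Wilcoxon Rank-Sum test assuming that the actual data distribution is normal". The inputs are 47 per group, a difference of 4.0, SD 7.4 in both groups and alpha 0.05, giving 81% power. The sentence before it frames the hypothesis as finding no "difference (defined as a change in NIHSS < 4) between NIHSS scores at 90 days".

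Section 10(b) splits the 117 subjects by enrolment severity: "39 subjects with moderate stroke = NIHSS 5-15; 39 subjects with moderate to severe stroke = NIHSS 16-20", and 39 with NIHSS 21-42. The Version 1.6 entry in section 2 gives the purpose of the bands: "Use predetermined enrollment caps of 39 subjects".

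On randomisation, section 10, item 3 says that "eligible subjects will be randomized into one of two arms: placebo or NAC", and section 18 refers to a log held in the ED pharmacy ("She will instruct other ED pharmacists about the study and the randomization log"). Neither mentions strata.

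Section 10, item 2 makes an NIHSS of at least 5 an eligibility requirement and says of the baseline assessments: "This data will be recorded for study purposes using a standard data collection sheet". The same scale is repeated at days 30 and 90.

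**The concern.** Filling three equal bands across NIHSS 5-42 builds a wide baseline spread into the trial. Whatever part of that spread persists to day 90 stays in the error variance of an unadjusted test. A test that conditions on enrolment NIHSS removes it. Because the covariate is measured before randomisation, on the same scale as the outcome and for everyone, using it needs no new data.

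What is at stake is power in a single-centre trial sized only just above its 0.80 target. If enrolment NIHSS predicts day-90 NIHSS even moderately, the gain is worth having. If it predicts weakly, almost nothing is lost. There is also a smaller risk of ambiguity: the word change in the hypothesis sentence could be taken to license a change-from-baseline analysis, which can be less powerful than no adjustment at all.

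**Working it through.** **Inputs from section 10(b):** 47 evaluable per arm; difference 4.0; SD 7.4; one-sided alpha 0.05; 117 enrolled; 25% loss, so 117 × 0.75 = 87.75, or about 44 per arm.

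**Assumed, because the documents do not give it:** the correlation r between enrolment and day-90 NIHSS, taken as 0.2 to 0.7.

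**Step 1: the plan's own figure.** For a rank-sum test on normal data, the effective size per arm is m = n × 3/π, with 2m − 2 degrees of freedom and noncentrality 4.0 / (SD × √(2/m)). With n = 47, m = 44.88 and the noncentrality is 4.0 / (7.4 × √(2/44.88)) = 2.56. The one-sided critical t is 1.66, and power is 81.5%. A simulated Mann-Whitney test (20,000 runs) gave 81.7%. The stated 81% reproduces. The two-sided equivalent is about 72%, so the figure is one-sided.

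**Step 2: adjusting for enrolment NIHSS.** Treating 7.4 as the total SD, the residual SD is 7.4 × √(1 − r²). The unadjusted size that would match 47 adjusted is 47 / (1 − r²).

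| r | Residual SD | Power, 47 per arm | Power, 44 per arm | Unadjusted n per arm equivalent to 47 adjusted |
|---|---|---|---|---|
| unadjusted | 7.40 | 81.5% | 79.2% | 47 |
| 0.2 | 7.25 | 82.9% | 80.6% | 49 |
| 0.3 | 7.06 | 84.6% | 82.4% | 52 |
| 0.5 | 6.41 | 90.1% | 88.3% | 63 |
| 0.7 | 5.28 | 97.2% | 96.4% | 92 |

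**Step 3: simulating the tests themselves.** 4,000 trials, 47 per arm, enrolment NIHSS in equal thirds uniform on 5-15, 16-20 and 21-31 (upper limit assumed), unstratified allocation.

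| Test | r = 0.2 | 0.3 | 0.5 | 0.7 |
|---|---|---|---|---|
| Plain Mann-Whitney | 83% | 83% | 83% | 82% |
| van Elteren by band | 83% | 85% | 89% | 95% |
| Rank ANCOVA on enrolment NIHSS | 84% | 86% | 90% | 97% |

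With integer scores floored at 0 (placebo latent mean 8), Mann-Whitney gave 80% throughout, and rank ANCOVA gave 81, 82, 88 and 96%. At r = 0, a separate run of 3,000 trials gave 81.3% for rank ANCOVA against 81.2% for Mann-Whitney, so the cost of an uninformative covariate is negligible.

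**Step 4: type I error** (8,000 null trials, nominal 5%). With unstratified allocation, all three tests gave 4.6-5.1%. With allocation stratified by band, at r = 0.3, 0.5 and 0.7, plain Mann-Whitney fell to 4.1, 3.0 and 1.4%. The van Elteren test stayed at 4.6-4.8% and rank ANCOVA at 4.5-4.6%. Stratifying the randomisation without adjusting the analysis therefore makes the test conservative.

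**Step 5: a change score instead.** Its SD is √(7.4² + 7.1² − 2 × r × 7.4 × 7.1), with baseline SD 7.1 assumed. At r = 0.2, 0.3, 0.5 and 0.7 this is 9.17, 8.58, 7.25 and 5.62, and power at 47 per arm is 66, 71, 83 and 96%. It beats no adjustment only when r exceeds 7.1 / (2 × 7.4) = 0.48.

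**Step 6: a different reading of 7.4, not to be combined with Step 2.** Suppose 7.4 is the SD within a band, band means are 10, 18 and 26 (variance 42.67), and a fraction k of that spread persists to day 90. The total SD is then √(7.4² + k² × 42.67), which is 7.7 at k = 0.3 and 8.7 at k = 0.7. Unadjusted power at 47 per arm is 79% and 70%. Simulated adjusted power returns to about 78-80%.

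**The case against.** The strongest reply is that nothing is broken. The planned test is valid under randomisation and meets the 0.80 target at 47 per arm, and the size of the gain rests on a correlation that the documents do not supply. Several features could lower that correlation. The intention-to-treat set may retain stroke mimics. For t-PA recipients the study infusion starts 24 hours after t-PA ends, so enrolment NIHSS is not their pre-infusion state. Excluding thrombectomy candidates may leave the severe band unfilled, which would narrow the spread. All of this is fair and is why the gain is given as a range that starts at 1 point. It does not change the direction. A further simulation with 117 enrolled, 25% loss (random or concentrated in the severe band) and floored integer scores still showed gains of about 1, 2, 8-9 and 17-18 points over the same values of r.

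The change-score reading is strained. Read whole, the sentence in 10(b) refers to a difference between arms at 90 days, and 10(e) agrees. This part stands only as a reason to state the point in a few words.

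Two further points are right. Deaths have no day-90 NIHSS, so any rank-based test, planned or proposed, needs a stated rule for ranking them; the calculations here do not model deaths. And absence cannot be fully proved, because some pages were not available for review. The contents page, however, lists no statistical section.

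**Conclusion.** The point holds as a recommended improvement, not an error. In the text available for review, the primary comparison makes no use of enrolment NIHSS or the severity bands. With 7.4 as the total SD and r between 0.2 and 0.7, pre-specified adjustment adds about 1 to 16 points of one-sided power at 47 per arm and about 1 to 17 at 44 per arm. At 44 per arm the unadjusted test, at 79.2%, falls just below the 0.80 target, and adjustment restores it even at r = 0.2.

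Confidence in the direction is high. Confidence in the size is moderate at best, because r is assumed and the documents do not show that 7.4, which section 10(b) links to earlier oral NAC work, fits a sample filled in equal thirds.

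**What to change.** Before unblinding:

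- Name the primary test as a baseline-adjusted comparison of day-90 NIHSS: rank-based ANCOVA on arm with enrolment NIHSS as a continuous covariate, or at least a van Elteren test stratified by the three bands.
- State that it is not a change-score analysis, and state how deaths are ranked.
- Keep the unadjusted Mann-Whitney test as a sensitivity analysis.
- State the randomisation method, and whether 7.4 is a total or a within-band SD.

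Optionally, if enough enrolment remains, randomise further subjects in permuted blocks within band. The primary analysis must then be adjusted, and the unadjusted sensitivity test should be read as conservative.

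The core change is analysis wording in a protocol amendment, with no new data and no more patients, and it gives most of the gain. Band-stratified randomisation is a design change whose practicality depends on enrolment status, which the documents do not give.

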4) Subjects will be contacted by telephone 24 hours post discharge, 3 days post discharge, and at 7 days to be monitored for adverse events and asked whether they have had any new symptoms or problems since the last study assessment. This will be an open question that will be recorded prospectively for each subject. If the subject reports an adverse event this is still present at the time of the phone call and wants to be further evaluated, they will be told to return to the emergency department and seen by a physician not associated with the investigation. Further the investigator from

PROTOCOL TITLE: Randomized Placebo Controlled Trial of Intravenous N-Acetylcysteine for the Treatment of Acute Ischemic Stroke

the team will also meet them in the Emergency Department to detail the information. All adverse events, whether they are deemed mild or serious, will be forwarded immediately to the Medical Monitor who will have discretion on whether to halt the study or continue. The Medical Monitor's reports will be forwarded to the Institutional Review Board (IRB). In addition, all unanticipated problems pose a risk to subjects or others will be reported to the Institutional Review Board (IRB) as required by FDA regulations. (There is no sponsor for this study, so no report needs to go to a sponsor).

4) Subjects will be instructed to return to the neurology clinic on day 30 and day 90 for re-evaluation. The same assessment will be performed as on day zero: the NIHSS and the MRS as well as the Glasgow Outcome Scale (GOS) and Barthel Index (BI). The GOS is a 5-point scale on which 5 indicates independence and 1 death. The BI assesses the ability to perform activities of daily living, on a scale that ranges from 0 (complete dependence on help with activities of daily living) to 100 (independence). These scores will be recorded on a standard data collection sheet. A representative from the neurology department will perform the examination, blinded from the previous scoring and treatment. In addition to the neurologic evaluation, patients will be queried at this time as to whether they experienced any nausea, vomiting, flushing, and itchiness, wheezing or difficulty breathing between the time of their discharge and the reevaluation.

For convenience, the 30 day follow up will have a tolerance range +/- 3 days and the 90 day follow up will permit +/- 10 day window.

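### NIHSS is scored at day 30, but no stated endpoint, analysis or missing-data rule uses it, although 25% loss is expected before the day-90 primary comparison

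*Combined protocol and SAP*

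**What the plan says.** Section 10 (Study Design) brings subjects back to clinic twice: "Subjects will be instructed to return to the neurology clinic on day 30 and day 90 for re-evaluation". At both visits, "The same assessment will be performed as on day zero: the NIHSS and the MRS" are scored, together with GOS and BI. Section 10(f) repeats this.

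Section 10(e) (Study Endpoints) defines the primary endpoint: "The primary study endpoint will be comparison between groups (NAC treated group versus treatment) of the NIHSS at 90 days". The secondary list begins "Secondary endpoints include changes in the MRS, GOS, BI, and blood tests at 30 days and 90 days" and adds MRI measures at day 90. NIHSS is therefore the only clinical scale scored at day 30 that is not named as a day-30 endpoint.

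The only statistical test named is in section 10(b), where the sample size rests on a "one-sided Mann-Whitney U or Wilcoxon Rank-Sum test". Loss is handled there by enrolling more: "Assuming a dropout rate of 25% or lost to follow-up, we would enroll 59 in each group for a total of 117".

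Section 10(k) says that subjects who do not complete the day-30 or day-90 follow-up will be withdrawn. Section 10(f), item 7, names a per-protocol and an intent-to-treat analysis but gives no rule for a missing day-90 NIHSS.

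**The concern.** A subject seen at day 30 and lost by day 90 has a score on the primary scale from two months earlier. Nothing in the plan lets that score inform the primary comparison. The plan names a day-90 rank test and withdraws those who miss a visit, with no method for missing values. The analysis that follows is one of day-90 completers.

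Two things are at stake. The smaller is precision, since the plan expects a quarter of subjects to be lost. The larger is bias. The trial enrols NIHSS 5 to 42 and takes its outcome at clinic visits, so attendance may well depend on disability. A completers-only comparison is safe only if loss is unrelated to outcome, and enrolling more subjects does not repair it when that fails.

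**Working it through.** **Inputs from section 10(b).** Difference 4.0, SD 7.4 in both groups, alpha 0.05 one-sided, rank-sum test under normality, 47 evaluable per group, 117 enrolled, 25% loss.

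**Inputs assumed, because the documents give neither.** *s* is the share of subjects lost at day 90 who did attend day 30. *ρ* is the correlation between day-30 and day-90 NIHSS.

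**1. The plan's own power.** With rank-sum efficiency 3/π under normality,

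power = Φ( 4 / (7.4 × √(2 / (n × 3/π))) − 1.645 ).

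For n = 47: Φ(2.561 − 1.645) = 0.820. A noncentral-t version gives 0.815 and a 20,000-run simulation 0.817. The stated figure, "achieve 81% power to detect a difference of 4.0", reproduces.

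**2. What 25% loss leaves.** 117 × 0.75 / 2 = 43.9 per arm, below the required 47, because 117 corresponds to 47 × 1.25 = 58.75 per arm and not to 47 / 0.75 = 62.7. For n = 43.9: Φ(2.474 − 1.645) = 0.797 (noncentral t 0.791). There is no spare margin.

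**3. What the day-30 score could add.** For two visits with loss between them, the large-sample effective size per arm is

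n_eff = 1 / [ (1 − ρ²)/43.9 + ρ²/(43.9 + 14.6 s) ],

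where 14.6 = 58.5 − 43.9 is the number lost per arm.

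| s | ρ | n_eff per arm | one-sided power |
|---|---|---|---|
| 0 | any | 43.9 | 0.797 |
| 0.3 | 0.5 | 44.9 | 0.805 |
| 0.3 | 0.7 | 45.9 | 0.812 |
| 0.5 | 0.7 | 47.2 | 0.821 |
| 0.5 | 0.8 | 48.3 | 0.829 |
| 0.7 | 0.5 | 46.1 | 0.813 |
| 0.7 | 0.9 | 51.8 | 0.852 |

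Over s = 0 to 0.7 and ρ = 0.5 to 0.9, power rises by 0 to 5.5 percentage points (0.852 − 0.797).

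**4. The gain with the method proposed.** The formula describes a likelihood estimate of a mean difference, not imputation followed by a rank test. That procedure was simulated with normal data, 58 per arm, Rubin pooling of the Mann-Whitney estimate, 1,500 runs and no baseline score in the imputation:

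| s | ρ | power, completers | power, imputed |
|---|---|---|---|
| 0.3 | 0.7 | 78.2% | 79.1% |
| 0.5 | 0.8 | 78.1% | 81.4% |
| 0.7 | 0.9 | 80.0% | 84.3% |

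Simulation error is about 1 point, so the gain is roughly 1 to 4 points in these three cases.

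**5. Bias.** In an illustrative simulation, loss rose with day-30 NIHSS to about 24% in the control arm and the true difference was 4. Completers-only gave about 3.7, and imputation within arm from day 30 gave 4.0. The loss pattern is assumed, so this shows the direction and not the size to expect here.

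**The case against.** The strongest reply is that the protocol is silent rather than wrong. A reader might infer that day-30 scores will be thrown away. No text says so, nor says that the primary analysis is restricted to completers. The secondary list is introduced with a word that need not be exhaustive. The lay summary (section 5) promises to look at benefit or harm over the course of the study, and an intent-to-treat analysis is named. This stands as far as wording goes: the documents support saying that use of the score is not specified, not that it is discarded. None of these statements, however, names day-30 NIHSS, a method or a rule, and section 10(k) points towards completers. Any later use would be post hoc.

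The second reply is that the power gain is small and uncertain. This also stands. Subjects who leave against advice or elope during the first admission, whom section 10(k) mentions, may have no day-30 score. If nobody lost at day 90 attended day 30, nothing is gained.

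The third is that imputation alone does not complete the primary analysis. The protocol gives death a value on MRS and GOS but none on NIHSS, and 39 of the 117 subjects are to have NIHSS 21–42. If deaths form part of the 25%, fewer than 14.6 per arm can be imputed and the gain shrinks. The fix must therefore cover deaths and the withdrawal rule.

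**Conclusion.** The point holds as one of specification and analysis choice. NIHSS at day 30 is collected, no stated endpoint or analysis uses it, and the absence of a missing-data method together with section 10(k) leaves a day-90 completers' comparison of about 44 per arm, with one-sided power of about 80%.

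A reader might infer a large recoverable loss of power. The figures do not support that. Under the assumed ranges the gain is 0 to about 6 points by formula, and likely somewhat less with imputation and a rank test. The stronger reason to act is bias: imputation replaces the assumption that loss is unrelated to outcome with the weaker one that it is random given arm, baseline NIHSS and day-30 NIHSS. The correlation, the share seen at day 30 and the number of deaths cannot be fixed from the documents.

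**What to change.** Before unblinding, write into the analysis plan:

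- Data already collected from subjects withdrawn for missing a visit stay in the intent-to-treat analysis; reconcile section 10(k) with this.
- For the primary day-90 comparison, multiply impute missing day-90 NIHSS in survivors, within arm, from baseline and day-30 NIHSS. Then apply the planned rank test with a stated pooling rule.
- Do not impute subjects known to have died; state how deaths are ranked in the test.
- Report completers only as a sensitivity analysis.

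Listing day-30 NIHSS as a secondary endpoint is optional. It would make the result visible but does not by itself recover day-90 information.

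The cost is wording and a little programming, with no new data. The downside is reliance on the missing-at-random assumption given baseline and day-30 NIHSS, which cannot be verified from the data.
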